Appendix A presents a list of the domains, their definitions, and survey items about hand-hygiene influencing.

The hand hygiene items will appear in a random order.

In the final survey, we aim to assess each of 11 behavioral determinates using at least 3 items that can be responded to with a 5-point Likert scales, where 1=strongly disagree and 5=strongly agree. Some items will be reverse scored to mitigate acquiescence bias.

- **Survey Section 4: Surface disinfecting.**

Appendix A presents a list of the domains, their definitions and survey items about hand-hygiene influencing.

The surface cleaning items will appear in a random order.

In the final survey, we aim to assess each of 11 behavioral determinates using at least 1 item that can be responded to with a 5-point Likert scales, where 1=strongly disagree and 5=strongly agree. Some items will be reverse scored to mitigate acquiescence bias.

- **Survey Section 5: Self-reported confidence (3 items).**

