## 12b. Statistical methods

As a reminder, the sample-size is designed to support a factor analysis for the hand-hygiene component of the project. The surface cleaning component of the project will only be analyzed using descriptive and exploratory methods.

Software: The data will be analysed using the most recently available copies of SPSS and SPSS: AMOS.

Descriptive: Frequencies, percentages, averages and confidence intervals will be used to describe the participants' responses and demographics.

Internal Consistency: Cronbach's alphas will be calculated. Items will be removed as necessary to achieve an alpha coefficient of 0.70 or above within each domain; those coefficients as low as 0.65 will be tolerated if necessary to retain the planned model.

[figure not shown]
Confirmatory Factor Analyses (CFA) - Objective 4: CFA will be performed to test whether the data from the items fit within the pre-determined components.

The first models (the primary analyses) will be conducted with the data from all the countries and then additional models (the secondary analyses) will be conducted with each country.

The models will be specified in AMOS and tested for goodness of fit using three indices: (a) absolute fit (based on a Chi-squared to degrees of freedom ratio, less than 2; ), (b) parsimony (based on Root Mean Square Error of Approximation (RMSEA) of close to or less than 0.06), and comparative fit (based on an index 'close to' 0.95; ). The models may be revised until the desired measures of fit are obtained.

Figure will be created to describe the final models' structure. An example of a figure like this with only 2 determinates appears below (Figure 2):

Figure 2. Example of a CFA model

Regression analyses - Objective 5: Multiple regression analysis will be conducted, overall and for each country. The predictors will be participants' average responses to each behavioural determinate, and the outcome will be participants' average responses to the confidence items. An alpha value of 0.05 will be used to assess each predictors' contribution to the overall model.

Exploratory Analyses - Objective 6: The participants' individual differences will be compared using graphical analyses (bar charts with error bars) and statistical tests (e.g., ANOVAs). Their content is not further specified within this protocol.

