Appendix A. Survey items (finalized 09-Apr-2020)

Domain	Question Number	Handwashing Surface Disinfection	Parents	Teachers
Knowledge An awareness of the existence of something	1	H	I know that my children should wash their hands with soap and water for at least 20 seconds.	I know that my pupils should wash their hands with soap and water for at least 20 seconds.
	2	H	(RS) I do not know when my children should wash their hands with soap and water.	(RS) I do not know when my pupils should wash their hands with soap and water.
	3	H	(RS) I know that when my children's hands look clean, they are germ free.	(RS) I know that when my pupils hands look clean, they are germ free.
	4	SD	(RS) I know that when surfaces look clean, there are no germs.	(RS) I know that when surfaces look clean, there are no germs.
	5	SD	I know which surfaces I should disinfect in the home.	I know which surfaces I should disinfect in the classroom
Skills An ability or proficiency acquired through practice	6	H	I am able to teach my children to wash their hands.	I am able to teach my pupils to wash their hands.
	7	H	I am able to help my children develop good handwashing habits.	I am able to help my pupils develop good handwashing habits.
	8	H	(RS) I am not able to teach my children to wash their hands.	(RS) I am not able to teach my pupils to wash their hands.
	9	SD	I have the ability to disinfect surfaces in the home.	I have the ability to disinfect surfaces in the classroom
	10	SD	(RS) I do not have the ability to disinfect some of the surfaces in the home.	(RS) I do not have the ability to disinfect some of the surfaces in the classroom
Memory, attention and decision processes The ability to retain information, focus selectively on aspects of the environment and choose between two or more alternatives	11	H	I remind my children to wash their hands before eating.	I remind my pupils to wash their hands before eating.
	12	H	(RS) I forget to remind my children to wash their hands.	(RS) I forget to remind my pupils to wash their hands.
	13	H	(RS) There are many distractions that cause me to forget to remind my children to wash their hands.	(RS) There are many distractions that cause me to forget to remind my pupils to wash their hands.
	14	SD	I remember to disinfect the surface areas in my home every day.	I remember to disinfect the surface areas in the classroom every day.

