	15	SD	(RS) I forget to disinfect the surface areas in my home.	(RS) I forget to disinfect the surface areas in the classroom .
Behavioural regulation Anything aimed at managing or changing objectively observed or measured actions	16	H	I check that my children have washed their hands before they eat food to encourage their future hand hygiene.	I check that my pupils have washed their hands before they eat food to encourage their future hand hygiene.
	17	H	(RS) I do not always check if my children wash their hands before eating food.	(RS) I do not always check if my pupils wash their hands before eating food.
	18	H	(RS) I do not always check if my children wash their hand after going to the toilet.	(RS) I do not always check if my pupils wash their hand after going to the toilet.
	19	SD	28. I keep track of whether I have disinfected surfaces in the home.	28. I keep track of whether I have disinfected surfaces in the classroom .
	20	SD	29. (RS) I don't keep track of whether I have disinfected surfaces in my home.	29. (RS) I don't keep track of whether I have disinfected surfaces in the classroom .
Social/professional role and identity A coherent set of behaviours and displayed personal qualities of an individual in a social or work setting	21	H	It is part of my role as a parent to teach my children to wash their hands.	It is part of my role as a teacher to teach my pupils to wash their hands.
	22	H	(RS) It is not my role in society to teach my children to wash their hands.	(RS) It is not my role in society to teach my pupils to wash their hands.
	23	H	(RS) It is not my role in society to tell my children to wash their hands.	(RS) It is not my role in society to tell my pupils to wash their hands.
	24	SD	It is my role as a parent in society is to disinfect surfaces in my home	It is my role as a teacher in society is to disinfect surfaces in my classroom
	25	SD	I feel a social responsibility to disinfect surfaces in my home.	I feel a social responsibility to disinfect surfaces in the classroom
Beliefs about capabilities Acceptance of the truth, reality, or validity about an ability, talent, or facility that a person can put to constructive use	26	H	I believe my children would listen to me if I taught them to wash their hands	I believe my pupils would listen to me if I taught them to wash their hands

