	27	H	(RS) I do not believe I can control whether my children wash their hands.	(RS) I do not believe I can control whether my pupils wash their hands.
	28	H	I believe that I can tell my children to wash their hands with soap and water.	I believe that I can tell my pupils to wash their hands with soap and water.
	29	SD	I believe that I am capable of disinfecting surfaces in my home.	I believe that I am capable of disinfecting surfaces in the classroom .
	30	SD	(RS) I believe that there is little I can do to disinfect surfaces in my home.	(RS) I believe that there is little I can do to disinfect surfaces in the classroom
Beliefs about consequences/ Optimism / Reinforcement (Belief) Acceptance of the truth, reality, or validity about outcomes of a behaviour in a given situation (Optimism) The confidence that things will happen for the best or that desired goals will be attained (Reinforcement) Increasing the probability of a response by arranging a dependent relationship, or contingency, between the response and a given stimulus	31	H	I believe that telling my children to wash their hands with soap and water will protect them from falling ill.	I believe that telling my pupils to wash their hands with soap and water will protect them from falling ill.
	32	H	(RS) I believe that children's handwashing habits have little effect on whether they get ill.	(RS) I believe that pupil's handwashing habits have little effect on whether they get ill.
	33	H	(RS) I believe that teaching my children to wash their hands is not worthwhile.	(RS) I believe that teaching my pupils to wash their hands is not worthwhile.
	34	SD	I believe that if I disinfect my home, my children will all fall ill less often.	I believe that if I disinfect the classroom my pupils will all fall ill less often.
	35	SD	(RS) I believe that disinfecting my home has no effect on how often my children get ill.	(RS) I believe that disinfecting my classroom has no effect on how often my pupils get ill.
	36	H	I intend to keep reminding my children to wash their hands before eating.	I intend to keep reminding my pupils to wash their hands before eating.

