Intentions / Goals (referred to as: action plans in Dyson et al) (Intentions) A conscious decision to perform a behaviour or a resolve to act in a certain way (Goals) Mental representations of outcomes or end states that an individual wants to achieve	37	H	I intend to keep reminding my children to wash their hands after going to the toilet.	I intend to keep reminding my pupils to wash their hands after going to the toilet.
	38	H	(RS) I do not intend to teach my children to wash their hands.	(RS) I do not intend to teach my pupils to wash their hands.
	39	SD	I intend to regularly disinfect surfaces in my home.	I intend to regularly disinfect surfaces in the classroom .
	40	SD	(RS) I do not intend to regularly disinfect surfaces in my home.	(RS) I do not intend to regularly disinfect surfaces in the classroom .
Emotion A complex reaction pattern, involving experiential, behavioural, and physiological elements, by which the individual attempts to deal with a personally significant matter or event	41	H	(RS) Teaching my children to wash their hands is frustrating.	(RS) Teaching my pupils to wash their hands is frustrating.
	42	H	(RS) Reminding my children to wash their hands is tedious.	(RS) Reminding my pupils to wash their hands is tedious.
	43	H	I enjoy praising my children for washing their hands.	I enjoy praising my pupils for washing their hands.
Environmental context and resources (Any circumstance of a person's situation or environment that discourages or encourages the development of skills and abilities, independence, social competence, and adaptive behaviour)	44	H	(RS) There is not enough time for my children to wash their hands.	(RS) There is not enough time for my pupils to wash their hands.
	45	H	There are practical resources available in my home for my children to wash their hands.	There are practical resources available in my school for my pupils to wash their hands.
	46	H	There are practical resources like running water, available in my home for my children to wash their hands.	There are practical resources like running water, available in my school for my pupils to wash their hands.
	47	SD	(RS) I don't have the time to disinfect surfaces in my home.	(RS) I don't have the time to disinfect surfaces in the classroom .

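### Every hand-hygiene domain mixes positive and reverse-scored items, but the planned CFA has no wording factor, so acquiescence could make a correct 11-factor structure miss the chi-square/df and CFI limits

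*Combined protocol and SAP*

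**What the plan says.** Section 11 (Survey Section 3) says of the hand-hygiene items that "we aim to assess each of 11 behavioral determinates using at least 3 items", on a 5-point agreement scale, and adds: "Some items will be reverse scored to mitigate acquiescence bias". The plan therefore expects this response style.

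Appendix A lists exactly three hand-hygiene items per domain. Those marked RS are mostly negated statements, for example ("RS) I do not know when my children should wash their hands with soap and water".

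Section 12b tests by CFA whether the items fall into the pre-determined components, first in all countries pooled (primary) and then in each country (secondary). There are three criteria: chi-square/df below 2, RMSEA close to or under 0.06, and a comparative index close to 0.95, which I take to be the CFI. The text mentions no wording factor, method factor or correlated errors. Its response to poor fit is: "The models may be revised until the desired measures of fit are obtained".

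**The concern.** Mixing item directions protects a domain average, because agreeing with everything pushes the two kinds of item in opposite ways. A CFA fits covariances, and there acquiescence remains after rescoring. It raises the covariance of items worded in the same direction and lowers that of items worded in opposite directions, across all domains at once. Factors defined by content cannot reproduce that pattern, so it shows up as misfit of the Theoretical Domains Framework (TDF) structure.

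This CFA is the primary analysis, and it is repeated by country. If fit is missed, the revision clause lets the analyst merge domains, drop items or add paths until the indices are met. A sound domain structure could be rejected or rewritten because of how people use an agreement scale. The revised domains would then supply the predictors for the regressions and inform the planned school intervention.

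**Working it through.** **Item directions (Appendix A, hand-hygiene items only).** RS items per domain, in Appendix A order from Knowledge to Social influences: 2, 1, 2, 2, 2, 1, 2, 1, 2, 1, 1. The sum is 17 of 33. Every domain is split 2:1.

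**Sample sizes (Table 2, quotas filled).** India 375 + 375 + 75 = 825. Each other country 225 + 225 + 75 = 525. Pooled 825 + 6 × 525 = 3,975.

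**Model size.** With correlated factors there are 33 loadings + 33 error variances + 55 factor covariances = 121 parameters, so df = 33 × 34/2 − 121 = 440. The plan states no parameter count or expected fit value, so there is no figure of its own to reproduce.

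**What acquiescence does.** Let s = +1 for a positive item and −1 for a reverse-scored item, and let a² be acquiescence's share of item variance. After rescoring, the covariance of items i and j is λ²φ + s_i s_j a², with φ = 1 within a domain. Of the 33 × 32/2 = 528 pairs, 136 + 120 = 256 share a direction and gain a², and 17 × 16 = 272 differ and lose it. With λ = 0.68, φ = 0.5 and a² = 0.05:
- within a domain, λ² = 0.4624 becomes 0.5124 (same direction) or 0.4124 (opposite);
- between domains, 0.2312 becomes 0.2812 or 0.1812.

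For any pair of domains, the plain model requires the nine cross-covariances to be products of loadings times one factor correlation. Adding the sign pattern breaks that form.

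**Fit.** I fitted the plain model by maximum likelihood to population matrices in which the 11-factor structure is exactly true. With F0 the minimum discrepancy, expected chi-square/df = 1 + (N − 1)F0/df, RMSEA = √(F0/df), and CFI = 1 − F0/F_baseline. Example (λ = 0.8, φ = 0.5, a² = 2%): F0 = 0.6538. Pooled chi-square/df is 1 + 3,974 × 0.6538/440 = 6.9; at N = 525 it is 1 + 524 × 0.6538/440 = 1.78. RMSEA is √(0.6538/440) = 0.039 and CFI is 0.963.

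For λ = 0.68, φ = 0.5:

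| Acquiescence share | chi-square/df, N = 3,975 | chi-square/df, N = 525 | CFI | RMSEA |
|---|---|---|---|---|
| 2% | 4.3 | 1.4 | 0.96 | 0.029 |
| 5% | 14.0 | 2.7 | 0.86 | 0.057 |
| 10% | 32.4 | 5.2 | 0.73 | 0.089 |

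Share at which each limit is crossed (λ = 0.6-0.8, φ = 0.5):

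| Limit | Share |
|---|---|
| chi-square/df, pooled | 0.7-1.2% |
| chi-square/df, India | 1.8-3.0% |
| chi-square/df, N = 525 | 2.4-4.0% |
| CFI 0.95 | 2.2-2.5% |
| RMSEA 0.06 | 3.7-6.3% |

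**Simulation check (λ = 0.7, φ = 0.5, 10 replicates per setting; continuous, symmetric 5-point and skewed 5-point responses).** With no acquiescence the plain model passes: chi-square/df 1.00-1.21, CFI at least 0.976. At 5% with 5-point responses, pooled chi-square/df is 10.2-12.2, CFI 0.874-0.876 and RMSEA 0.048-0.053. With one equal-loading wording factor added (df 439), chi-square/df at 2-5% is 0.96-1.22 and CFI at least 0.980.

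**The case against.** **Mild acquiescence does not fail every limit.** A reader might infer that it does. At 2%, a country model with N = 525 has chi-square/df 1.4, CFI 0.96 and RMSEA 0.029, all acceptable. Only the pooled chi-square/df clearly fails, and part of that is sample size: at N = 3,975 a ratio below 2 requires RMSEA below √(1/3,974) = 0.016, so almost any small misfit breaches it. This objection stands. CFI is not driven by N in that way, however, and still drops below 0.95 from about 2-2.5%.

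**The alpha rule does not reliably remove the odd-direction item.** Section 12b says "Items will be removed as necessary to achieve an alpha coefficient of 0.70 or above within each domain", and a reader might infer that this strips out the single minority-direction item in each domain. At λ = 0.68 and 5% acquiescence, the mean inter-item covariance is (0.5124 + 2 × 0.4124)/3 = 0.4457, so alpha is 3 × 0.4457/(1 + 2 × 0.4457) = 0.707. Deleting the minority item lowers it to 2 × 0.5124/1.5124 = 0.678. At 10% deletion would raise alpha from 0.693 to 0.720. But 12b tolerates values down to 0.65 to keep the planned model, and the three-item minimum, with exactly three items per domain, weighs against any deletion. The inference is not supported.

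**The key input is assumed.** The documents give no acquiescence estimate and no pilot results, and nothing in them shows that response style differs between the seven countries. Both limits stand.

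**The remedy check is circular.** A wording factor fitted to data generated with one must fit. The check shows that the model is identified and recovers the effect, not that it will fit real responses.

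**The plan already permits a wording factor.** The revision clause does not exclude one. It permits changing the domains just as readily, and a model chosen after seeing misfit is not pre-specified.

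**Conclusion.** The point holds as a risk, not a prediction. If acquiescence exceeds about 1% of item variance, a correct TDF structure would be expected to miss the pooled chi-square/df limit. Above about 2-2.5% it would also have CFI below 0.95, and above about 2.4-4% the N = 525 country models would miss chi-square/df too. RMSEA is the most tolerant index, staying at or under 0.06 until about 4-6%.

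These thresholds assume a true 11-factor model, equal loadings of 0.6-0.8, factor correlation 0.5, acquiescence acting equally on all items, and full recruitment. Letting the factor correlation vary from 0.3 to 0.7 does not change the picture: at 5%, pooled chi-square/df is 10.9-23.7, chi-square/df at N = 525 is 2.3-4.0, CFI is 0.81-0.89 and RMSEA is 0.050-0.076.

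The item set contains the mixed wording needed to separate response style from content, but the stated analysis does not use it. The improvement is cheap and needs no new data.

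**What to change.** In section 12b, name one second CFA model in advance:

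- the 11 domain factors plus one wording factor, uncorrelated with them;
- wording loadings fixed at +1 for positive items and −1 for reverse-scored items after rescoring, with one free variance;
- fitted to the pooled data and in each country, and reported beside the plain 11-factor model on all three indices;
- consulted before any other revision, so that a miss which disappears when wording is modelled is not met by changing domains or items.

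The estimated wording variance would also supply the acquiescence level that the documents lack, overall and by country.

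The cost is one extra parameter (122 instead of 121) and one extra AMOS run per sample. The downsides are two sets of fit indices to report and the simplification of equal wording loadings. The factor will not absorb other misfit, such as that from near-duplicate items (for example 22 and 23, or 45 and 46), and it does not cure the strictness of chi-square/df < 2 at the pooled sample size.

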Appendix A also includes three self-confidence items.

The first item regards participants' confidence about how often their children clean their hands when they are present, 0% to 100% of the time. The second item regards participants' confidence about how often their children clean their hands when they are not present, 0% to 100% of the time. The third item regards participants' confidence about how often they clean their own hands, 0% to 100% of the time.

*Translation.*

After creating the initial items in the English language, the research team will ask OpinionHealth to translate them. The same process will occur for the information/consent sheet. The translation process will proceed as describe in Table 1.

Table 1. Translation process

Step	Action
1	The research team will provide OpinionHealth with the initial items.
2	OpinionHealth will translate the items into the non-English language(s)
3	OpinionHealth will back-translate the items to English.
4	OpinionHealth will provide the research team with copies of the translated and back-translated items.
5	The research team will check to be sure that the items' intended meanings have not been lost in translation. If items' meaning are lost, the translation process will be repeated with those items.

---

Opinion is a reputable survey company located in the United Kingdom experienced in conducting online surveys in line with all UK and EU regulations and Market Research Society's Code of Conduct, e.g., GDPR. For more information, a link to Opinion Health's website is provided here:  
[http://opinionhealth.com/about\\_us](http://opinionhealth.com/about_us)

*Active survey.*

OpinionHealth will to recruit participants according to a stratified fashion across countries and demographic characteristics, see Table 2.

Table 2. Participants stratified characteristic

Country	Participants
India	375 mums 375 dads 75 teachers
UK	225 mums 225 dads 75 teachers
China	225 mums 225 dads 75 teachers
Australia	225 mums 225 dads 75 teachers
South Africa	225 mums 225 dads 75 teachers
Indonesia	225 mums 225 dads 75 teachers
Saudi Arabia	225 mums 225 dads 75 teachers

The first screen of the online survey will inform participants of the study and request their informed consent to take part (see Appendix B). Those who give their informed consent will continue. Participants who complete the survey will be issued with payment to compensate them for their time in an amount equal to approximately 1 GBP in their home countries currency (varies depending on exchange rates), which they can redeem in the form of amazon gift vouchers or via their personal PayPal accounts.

We will stop collecting survey responses in each country after the planned-sample sizes are achieved or 30 days have passed since that country's survey was activated, whichever comes first.

